6.13.2. Adverse Events

The Common Terminology Criteria for Adverse Events (CTCAE) version 4 will be used to report adverse events in CTCAE terms. The current MedDRA Version 14.0 (or higher) at the time of reporting will be used when reporting adverse events by MedDRA terms. The MedDRA Lower Level Term (LLT) will be used in the treatment-emergent computation.

Treatment-emergent adverse events (TEAE) are defined as follows:

- Any event that first occurred or worsened in severity after baseline, based on the MedDRA LLT term and CTCAE severity grade. This means that any episode of the same AE with the same grade as at baseline that starts after the first dose of study treatment will not be defined as treatment emergent, even if now considered possibly drug related.
- Or any PEC (emerged prior to informed consent) or any AE (emerged after signed informed consent) that were still present prior to first dose but has increased in severity (CTCAE grade) following the start of treatment, regardless of causation.

A listing of all adverse events by patient, including pre-existing conditions, will be presented. This listing will include patient number, adverse event (actual term, CTCAE term, and preferred term), event start and end dates, CTCAE grade, relationship to study drug/procedure, seriousness, and outcome. A listing of SAE will be produced using the similar format.

An overall summary will be provided for possibly drug-related AEs. The number and percent of evaluable patients will be summarized by treatment for each category below.

- Patients with at least one AE
- Patients with at least one TEAE
- Patients with at least one grade 3 or 4 AE
- Patients with at least one SAE
- Patients who discontinued due to AE
- Patients who discontinued due to SAE
- Patients who died on therapy
- Patients who died within 30 days of last dose of study drug (LY2157299/placebo or lomustine)

The AEs deemed by the investigator to be possibly related to study drug will be summarized separately for both MedDRA and CTCAE dictionaries, by their respective System Organ Class (SOC) terms and by decreasing frequency of their respective Preferred Term (PT) or CTCAE term within SOC. These summaries will be repeated for events regardless of study drug causality. Incidence rates of these events will be compared between treatment arms using Fisher's exact test. These analyses and summaries will be repeated for TEAEs. The SAEs will be summarized by MedDRA PT and CTCAE term by decreasing frequency within each SOC, regardless of causality.

The CTCAEs, separated by those defined as laboratory and non-laboratory CTCAEs, will be summarized by CTCAE term and maximum CTCAE grade, including the total for maximum Grade 3 and 4. These summaries will be provided for events regardless of study drug causality, and repeated for events deemed by the investigator to be possibly related to study medication. These summaries will be repeated for TEAEs.

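### The severe adverse event total in the maximum-grade tables stops at Grade 4, so it falls when an event becomes fatal, and no Grade 3-or-higher count is planned

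*SAP*

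**What the plan says.** The grading scale is fixed in SAP 6.13.2: "The Common Terminology Criteria for Adverse Events (CTCAE) version 4 will be used to report adverse events in CTCAE terms". Two kinds of severity summary follow in that section.

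- **Maximum-grade tables.** Laboratory and non-laboratory events are "summarized by CTCAE term and maximum CTCAE grade, including the total for maximum Grade 3 and 4". The tables are produced regardless of causality, for possibly related events, and again for treatment-emergent events. Protocol 12.2.10 defines the same subtotal.
- **Overview.** "An overall summary will be provided for possibly drug-related AEs", with one row for "Patients with at least one grade 3 or 4 AE". Other rows include "Patients with at least one SAE", "Patients who died on therapy" and "Patients who died within 30 days of last dose of study drug".

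Neither document mentions a Grade 5 adverse event or plans a Grade 3-to-5 total. Deaths and their reasons are listed and summarised by period in SAP 6.13.3. The listing in SAP 6.13.2 carries the grade and outcome of every event.

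**The concern.** A severity total should not improve when a patient's outcome gets worse. A total restricted to maximum Grades 3 and 4 does so: a patient moves out of it at the moment a Grade 4 event turns fatal. If fatal events differ between arms, the arm with more of them has the more understated severe total for the terms concerned.

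Comparing the safety of the two LY2157299 arms with lomustine plus placebo is a secondary objective (Protocol 6.2, SAP 4.2). Protocol 8.1 also wants to know whether the monotherapy toxicity profile merits further study. Readers will look at a severe-event total for both purposes. Protocol 10.3.1.1 expects major cardiovascular events and serious infections in this population, and such events can be fatal.

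**Working it through.** The plan states no figure for this point, so there is none to reproduce. The check is which patients each count includes. It rests on one fact about the scale that the documents do not spell out: Grade 5 in CTCAE version 4 means death from the event.

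**Maximum-grade total.** For one term in one arm, let n3, n4 and n5 be the numbers of patients whose maximum grade is 3, 4 and 5.

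- Planned total: T = n3 + n4.
- Grade 3 or higher: U = n3 + n4 + n5.
- Shortfall: U − T = n5, which is every patient with a fatal event of that term.

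If one Grade 4 patient's event becomes fatal, n4 falls by 1 and n5 rises by 1. The planned total becomes n3 + (n4 − 1) = T − 1. The Grade 3-or-higher total becomes n3 + (n4 − 1) + (n5 + 1) = U, unchanged.

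**Overview row.** This is an at-least-one count, so the worst grade does not decide membership. Let A be the patients with any recorded Grade 3 or 4 event and F those with a Grade 5 event, within the scope of the overview.

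- Planned row: |A|.
- Grade 3 or higher: |A| + |F| − |A and F|.
- Shortfall: |F| − |A and F|. This is zero if every patient with a fatal event also has a Grade 3 or 4 record, and |F| if none has.

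| Patient | Overview row | Maximum-grade total for the fatal term |
|---|---|---|
| Only severe record is Grade 5 | Missed | Missed |
| Grade 5 for one term, Grade 3 or 4 for another | Counted | Missed (counted under the other term) |
| One event at Grade 3 or 4 that worsens to Grade 5 | Counted only if the earlier grade is kept as a record | Missed |

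**Can the missing count be rebuilt?**

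- Within one term, yes by hand, if the table prints a Grade 5 category, because maximum-grade categories do not overlap. The plan does not say that it will be printed.
- At patient level, no. One patient can appear under several terms, so terms cannot be added. The overview needs |F| and |A and F|, and no row gives either.
- The death rows are not |F|. Protocol 12.2.10 has the overview repeated regardless of causality, so on-therapy deaths there can include progression deaths. Protocol 10.3.1.1 keeps those out of SAE reporting unless the drug may have contributed.
- The SAE row also counts non-fatal events such as hospitalisations, so it is not a severity count.

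**The case against.** The strongest reply is that nothing fatal is hidden. The maximum-grade tables are broken down by grade, with the 3-and-4 subtotal as an addition, so Grade 5 would naturally appear as its own category. SAEs are tabulated by term regardless of causality. All adverse events are compared between arms by Fisher's exact test without a grade restriction. Deaths have their own rows and a summary of reasons, and the listings give grade and outcome. No visible decision rule uses the severe subtotal. All of this stands, and it is why the point is small. It does not supply the missing count.

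Three stronger readings are tempting, and the documents do not support them.

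- *Patients whose worst event was fatal drop out of every severe count.* This is true of the maximum-grade total for the fatal term. It is not true in general of the overview row, which keeps anyone with another recorded Grade 3 or 4 event. Protocol 5.3 describes bone-marrow suppression as a common and severe effect of lomustine, so such overlap is plausible in two of the three arms.
- *The under-count can be put at some percentage.* That needs a fatal event rate, a severe event rate and their overlap. The documents give none of these. A figure built on assumed rates with no overlap would be an upper bound for the overview row.
- *The drug's aneurysm risk makes the gap serious here.* Protocol 5.6.4.1 draws that risk from continuous dosing in animals, calls its likelihood in humans unknown, and reports the move to intermittent dosing, which this trial uses. Protocol 5.7 reports no medically significant cardiovascular toxicity in Part A of the earlier study. A fatal case would also appear by term in the SAE tables.

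**Conclusion.** The point holds as a minor reporting-definition gap. The severe total in the maximum-grade tables excludes every patient whose maximum grade for the term is 5. The overview row excludes only those whose severe events were recorded at Grade 5 alone. The resulting bias in the severe total is downward.

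Its size per arm is n5 for each term in the tables, and between zero and the number of patients with a fatal event in the overview. The documents do not allow either to be turned into an expected number, or into an effect on the comparison between arms. The conclusion assumes only that Grade 5 is the fatal grade and that the table programs follow the text as written. The primary overall survival analysis does not depend on it.

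**What to change.** In SAP 6.13.2, and in the matching sentence of Protocol 12.2.10, define the subtotal in the maximum-grade tables as *Grade 3 or higher (Grades 3, 4 and 5)*. Make the same change to the overview row in SAP 6.13.2. State that Grade 5 is also shown as its own category. A Grade 3-and-4 subtotal can stay beside it if the sponsor wants continuity with other studies.

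No new data are needed, because Protocol 10.3.1 already has the CTCAE grade collected for every event. The cost is a few words and revised table shells. Protocol 12.2.1 requires an amendment only when a principal feature changes, so the SAP can carry and justify the revision if the protocol is not otherwise being reopened.

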6.13.3. Deaths, Other Serious Adverse Events, and Other Notable Adverse Events

All deaths in this study, including the reasons for death, will be listed by treatment. The reasons for death will be also summarized separately for on-therapy, within 30 days of last dose of study drug and during the long term follow-up periods.

6.13.4. Clinical Laboratory Evaluation

Listings of all laboratory results will be provided (using SI units [International System of Units], when available) by treatment, separately for hematology, chemistry, urinalysis, special chemistry, ECG chemistry, immune phenotype, whole blood for Fox3p, and urine C-terminal telopeptides of Type 1 collagen. Normal reference ranges, percent of the result outside of range (result divided by lower limit if result is less than lower limit; result divided by higher limit if result is greater than higher limit) and percent change from baseline will also be included.

A calculated CTCAE grade using CTCAE version 4 will be provided for all laboratory results which can be used independently of clinical judgment to determine a CTCAE severity grade. These summaries will be repeated for abnormal laboratory results.

The CTCAE term will be summarized by CTCAE grade in separate tables, linking these AEs to the laboratory term.

6.13.5. Vital Signs and Other Physical Findings

Vital signs measurements including height, weight, respiratory rate, temperature, blood pressure and post-baseline ECOG performance status will be listed by treatment arm.

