Efficacy: The primary analysis is to compare the HR between LY2157299 monohydrate plus lomustine therapy with lomustine plus placebo therapy based on OS using a Bayesian OS model which augments current control data with additional information from historical data. The same Bayesian OS model will be used to estimate the HR between LY2157299 monohydrate monotherapy and lomustine plus placebo therapy. Hazard rates and ratios of and between the 3 treatment arms will also be estimated for PFS. Response rates based on the RANO criteria will be estimated.

Safety: Summary statistics, plots, and listings for all safety data will be provided. Summaries of both acute toxicity (occurring in the first 3 cycles) and chronic toxicity will be provided by treatment arm.

Health Outcomes: Neurocognitive function will be compared to population norms, summarized for each assessment period, and change over time will be explored. Time-to-neurocognitive progression will be assessed between arms. Data from the MDASI-BT will be summarized for each assessment period. This summary will include descriptive statistics and change from baseline (including time to worsening of symptoms). The MDASI-BT will be reported as core symptoms, brain tumor symptoms, symptom interference, and symptom groupings.

Pharmacokinetic (PK): Exposure of LY2157299 monohydrate using population PK analysis will be compared. This analysis will explore the impact of covariates, such as demographic factors, on the relevant PK parameters. Exploratory PK/PD analyses may be conducted to identify the exposure-biomarker response (such as S100 β and LDH) relationship.

Pharmacodynamic (PD): Tumor tissue for pSMAD, MGMT promoter status, and serum assessments for S100 β , LDH, and T regulatory cells will be collected and correlated with clinical benefit.

Translational Medicine: Previously described genetic profile signatures will be studied for their relevance to the clinical outcome of LY2157299 monohydrate monotherapy or LY2157299 monohydrate plus lomustine and to the clinical outcome of recurrent malignant glioma.

3. Table of Contents

A Phase 2 Study of LY2157299 Monohydrate Monotherapy or LY2157299 Monohydrate plus Lomustine Therapy compared to Lomustine Monotherapy in Patients with Recurrent Glioblastoma

Section	Page

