5.6.3. Nonclinical Toxicology of LY2157299

The toxicity of LY2157299 has been characterized in repeat- and intermittent-dose nonclinical safety studies up to 6 months duration in the rat and dog.

For additional information see Section 5 in the IB and the following brief summary:

The heart and great vessels are major target organs for toxicity in both F344 rats and beagle dogs following treatment with LY2157299. These effects include valvulopathy and vascular lesions of multiple blood vessels at the base of the heart in rat and dog, which in the rat appear to be partially reversible.

Changes in the base of the ascending aorta, characterized by minimal-to-marked degeneration, disorganization, and separation of intramural elastic laminae without an accompanying inflammatory response, were observed in the dog administered daily doses of CCI mg/kg for 6 months. The aortic mural degeneration was focally extensive or multifocal with no compound-related microscopic changes in the descending aorta. Although the microscopic changes likely compromised regional aortic structural integrity, there were no changes diagnostic of an aortic aneurysm, no gross dilation, no effects in the intimal layer, and a lack of free blood within the wall of the aorta. A cardiac valvulopathy, characterized by endothelial/stromal cell proliferation, inflammation, and increases in smooth muscle actin immunolabeling and hemorrhage is similar in rats and dogs. The cardiac valvulopathy observed in preclinical toxicology species has not been associated with extracardiac evidence of valvular insufficiency or dysfunction.

The no-observed-effect level (NOEL) for cardiac effects in the rat is **[REDACTED]** mg/kg administered on a 2-week-on/2-week-off schedule and 8 mg/kg in the dog in the 6-month study.

Administration of LY2157299 may produce dose-dependent hemodynamic side effects, measured by decreased blood pressure and increases in heart rate, which can be easily monitored in the clinic and are reversible upon cessation of treatment. The nonclinical data do not reveal any substantive clinical risk of QT/corrected QT interval (QTc) prolongation at doses that result in total plasma concentrations of at least **[REDACTED]** μ g/mL.

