9.1. Treatments Administered

The following treatments will be administered in this study:

- LY2157299 Monotherapy:
 - LY2157299 300 mg/day, given orally as three 50-mg tablets BID for 14 days, followed by 14 days of rest, equaling a 28-day cycle.
- LY2157299 plus lomustine therapy:
 - The first lomustine dose will be given as 100 mg/m².
 - Remaining doses (starting with the second lomustine dose) are based on the investigator's discretion and will be given orally once every 6 weeks at 100 to 130 mg/m².
 - LY2157299 300 mg/day, given orally as three 50-mg tablets BID for 14 days, followed by 14 days of rest, equaling a 28-day cycle.
- Lomustine plus placebo therapy:
 - The first lomustine dose will be given as 100 mg/m².
 - Remaining doses (starting with the second lomustine dose) from 100 to 130 mg/m² are based on the investigator's discretion and will be given orally once every 6 weeks..
 - LY2157299 -matched placebo, given orally as 3 tablets BID for 14 days, followed by 14 days of rest, equaling a 28-day cycle.

Lomustine doses should be rounded to the lowest available capsule strength.

Weight is used to determine dose and should be assessed at each cycle, and dose should be recalculated for each cycle.

The investigator or his/her designee is responsible for the following:

- explaining the correct use of the drug(s) and planned duration of each individual's treatment to the patient/site personnel,
- verifying that instructions are followed properly,
- maintaining accurate records of study drug dispensing and collection,
- and returning all unused medication to Lilly or its designee at the end of the study.

Note: In some cases, sites may destroy the material if, during the investigator site selection, the evaluator has verified and documented that the site has appropriate facilities and written procedures to dispose clinical trial materials.

Patients will be instructed to contact the investigator as soon as possible if they have a complaint or problem with the study drug so that the situation can be assessed.

To be considered compliant, the minimum planned treatment of LY2157299 is 10 days and a maximum of 14 days per 28-day cycle and at least cc1% of the allocated LY2157299 prescribed dose has to be administered within each cycle.

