Attachment 1. JBAL Study Schedule

Study Schedule for Protocol H9H-MC-JBAL – Prestudy and Cycle 1

Cycle	Prestudy			Cycle 1								Comments
	Relative Day	≤28	≤14	≤7	1	3	7±2	12±2	14	15	16	26±2
Treatment												
Lomustine						X						
LY2157299 monohydrate or matched placebo				X	X	X	X	X				CCI
Procedures												
Informed consent	X											
Medical history		X										
Pregnancy test		X										CCI
Physical Examination		X		X								
Vital signs (heart rate, blood pressure)		X		X								
CTCAE		X		X								
Concomitant medications		X		X								

Cycle	Prestudy			Cycle 1							Comments	
	Relative Day	≤ 28	≤ 14	≤ 7	1	3	7 ± 2	12 ± 2	14	15	16	
Relative Day	≤ 28				1	3	7 ± 2	12 ± 2	14	15	16	26 ± 2
Within a Cycle												
ECOG performance status		X		X								
Health outcome measures		X									X	
Imaging Procedures												
Echocardiography with Doppler		X										
Radiological tumor assessment		X										
Chest CT scan or chest MRI		X										
Laboratory/Diagnostic Tests												
PFT			X									
ECG		X		X	X			X	X		X	
Troponin I and BNP			X								X	
Hematology			X								X	
Urinalysis			X								X	
Fox P3			X									

CCI

Cycle	Prestudy			Cycle 1							Comments	
	Relative Day	≤ 28	≤ 14	≤ 7	1	3	7 ± 2	12 ± 2	14	15	16	
Relative Day	≤ 28	≤ 14	≤ 7		1	3	7 ± 2	12 ± 2	14	15	16	26 ± 2
Serum chemistry			X								X	
ECG chemistry		X		X	X			X	X			
Serum hs-CRP			X									X
PK sampling				X	X			X	X	X		
CSF												
MAP				X			X					
Affymetrix				X								
Whole blood for PGx		X										
Whole blood/plasma				X								
Tumor tissue		X										

Study Schedule for Protocol H9H-MC-JBAL – Cycles 2, 5, 8, 11

Cycle	Cycles 2, 5, 8, 11					Comments
Relative Day Within a Cycle	1±2	6±2	12±2	21±2	26±2	
Treatment						
Lomustine				X		
LY2157299 monohydrate or matched placebo	X	X	X			
Procedures						
Physical examination	X		X			
Vital signs (heart rate, blood pressure)	X					
CTCAE	X					
Concomitant medications	X					
ECOG performance status	X					
Health outcome measures					X	
Echocardiography with Doppler					X	
ECG					X	
Tropionin I and BNP					X	
Hematology					X	
Urinalysis					X	
Fox P3					X	
Serum chemistry					X	

CCI

ECG chemistry					X	
Cycle	Cycles 2, 5, 8, 11					Comments
Relative Day Within a Cycle	1±2	6±2	12±2	21±2	26±2	
Serum hs-CRP					X	
Radiological tumor assessment					X	CCI
MAP			X			
Affymetrix					X	

Study Schedule for Protocol H9H-MC-JBAL – Cycles 3, 6, 9, 12

Cycle	Cycles 3, 6, 9, 12				Comments

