6.13.6. Electrocardiograms

Electrocardiogram (ECG) assessment of normality and clinical significance will be listed by treatment group. Myocardial information and quantitative results including PR, QRS, QTcB (Bazett's correction), QTcF (Fridericia's correction) and RR intervals will be provided in patient listings. In addition, listings and summaries of outlying corrected QT intervals (QTc, QTcB and QTcF) will be provided for each scheduled time point.

Baseline ECGs are ECGs performed either during screening or predose during the study. Changes in QT from baseline, delta QT, will be calculated by subtracting the respective reading taken at the same nominal time during screening from the reading taken after LY2157299 dosing on specified days as per protocol schedule. Similarly, changes in RR from baseline (ie. delta RR) will be calculated. Delta QT will then be analyzed using a linear mixed-effects model with treatment arm, timepoint and delta RR as fixed effects, treatment-by-time interaction and patient as a random effect (Dmitrienko and Smith 2003). Least square means by timepoint and treatment arm together with 90% confidence intervals will be provided. Mean differences and 90% confidence intervals between treatment arms will be estimated from the model.

If data warrant, additional exploratory analyses may be conducted using appropriate modeling techniques.

The ECG chemistry laboratory values will be listed and summarized separately from other laboratory values.

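### The SAP plans no summary of blood pressure and no between-arm estimate of heart rate, although the protocol flags both as possible drug effects and on-drug ECG data will exist

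*SAP*

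**What the plan says.** Protocol 5.6.3, in the nonclinical toxicology summary, states: "Administration of LY2157299 may produce dose-dependent hemodynamic side effects, measured by decreased blood pressure and increases in heart rate". It describes these effects as ones "which can be easily monitored in the clinic and are reversible upon cessation of treatment".

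The Attachment 1 row begins "Vital signs (heart rate, blood pressure", so heart rate and blood pressure are the two vital signs the schedule names. Its visible marks are prestudy, Cycle 1 Day 1, Day 1±2 of later cycles, and Visit 801.

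SAP 6.13.5 consists of one sentence: "Vital signs measurements including height, weight, respiratory rate, temperature, blood pressure and post-baseline ECOG performance status will be listed by treatment arm". It specifies no summary, change from baseline or comparison. The protocol synopsis, however, says: "Summary statistics, plots, and listings for all safety data will be provided". SAP 6.13, the parent section, also says that safety data will be summarized by arm as well as listed, with details to follow in its subsections.

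SAP 6.13.6 calculates the change from baseline in RR interval. Change in QT is then analyzed in a "linear mixed-effects model with treatment arm, timepoint and delta RR as fixed effects", plus a treatment-by-time interaction and a random patient effect. Least-squares means and arm differences with 90% confidence intervals are reported for QT.

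**The concern.** The protocol singles out two haemodynamic effects to watch for, and the trial has a blinded placebo comparison that could estimate them. Both lomustine arms receive lomustine, so LY2157299 against placebo is the randomized difference between them. Evaluating safety relative to lomustine plus placebo is a stated secondary objective.

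Followed as written, the analysis yields patient-level listings of blood pressure and RR, but no table or estimate showing whether either differs by arm. A modest average fall in blood pressure or rise in heart rate is hard to see in a listing. It is also the kind of effect that adverse-event counts miss.

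**Working it through.** No sample size, power or event figure bears on this point, so there is no plan figure to reproduce. The check sets reading times against dosing times, then sets the data collected against the analyses planned.

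**1. When readings fall relative to dosing.** Protocol 9.1 gives LY2157299 or placebo "BID for 14 days, followed by 14 days of rest, equaling a 28-day cycle". The last scheduled dose is on Day 14, and Day 1 of the next cycle is Day 29 on the same count.

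| Reading | Nominal time | Relation to LY2157299/placebo |
|---|---|---|
| Vital signs, prestudy | before Cycle 1 | before any dose |
| Vital signs, Cycle 1 | Day 1 | on drug only if taken after the dose; not visible |
| Vital signs, Cycle 2 on | Day 1±2 | 29 − 14 = 15 days after last dose (13 to 17) |
| Vital signs, Visit 801 | about 30 days after discontinuation | off drug |
| Blood pressure at echocardiography (Attachment 6), Cycle 2 on | Day 26±2 | 26 − 14 = 12 days after last dose (10 to 14) |
| ECG, Cycle 1 (Attachment 3) | Day 1 predose | before any dose |
| ECG, Cycle 1 | Day 1 at 3.5–5 h; Day 3 predose; Day 14 predose; Day 14 at 3.5–5 h | on treatment |
| ECG, Cycle 1 | Day 15 morning | morning after the last dosing day |
| ECG, Cycle 2 on | Day 26±2 | 12 days after last dose (10 to 14) |

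No visible vital-sign mark is nominally placed on Days 2 to 14 of any cycle. Blood pressure has at most one nominal on-drug reading, on Cycle 1 Day 1. The late side of the Day 1±2 window could put some later readings after dosing has restarted, as late as Day 3. Heart rate is better served: four of the six ECGs in Attachment 3 are on treatment.

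**2. What is planned for the data.**

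- Blood pressure: listed (SAP 6.13.5). No summary is specified. SAP 6.13.7 does not name the pressure taken at echocardiography.
- Heart rate as a vital sign: collected in Attachment 1, not named in SAP 6.13.5.
- RR interval: listed. Its change from baseline is calculated and enters the QT model as a covariate.
- Protocol 12.2.10 and 12.2.10.1 add no vital-sign analysis.

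By contrast, SAP 6.13.8 both lists and summarizes changes in pulmonary function by arm.

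**3. What the QT model can deliver.** With change in RR on the right-hand side, the arm effect is the QT difference at a given RR change. The arm difference in RR itself is not an output of that model, and no other specified analysis produces it.

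**4. What adverse-event analysis can deliver.** Protocol 10.3.1 asks sites to report vital-sign findings that are clinically significant and lead to a diagnosis. SAP 6.13.2 compares incidence by Fisher's exact test. A mean shift below the reporting threshold does not enter that comparison.

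Arm sizes are redacted and no standard deviation for RR or blood pressure is given, so the precision of the missing estimate cannot be stated.

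**The case against.** A reader might infer that the haemodynamic effect will go unreported, or that a real effect would look like none. The documents do not support that. Blood pressure and RR are listed, change in RR is calculated, and hypotension or tachycardia reported as adverse events would be compared between arms. The synopsis and SAP 6.13 contain general promises of summaries, so SAP 6.13.5 can be read as under-specified. Its list is introduced non-exhaustively, so heart rate is not formally excluded.

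The 5.6.3 statement is nonclinical and says only that the drug may have these effects. Protocol 5.7 reports no medically significant cardiovascular toxicity in patients in the earlier monotherapy study. Using change in RR as a covariate is a reasonable way to account for heart rate in a QT model and is not a fault. SAP 6.13.6 also allows further exploratory modelling.

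The schedule's Comments column is redacted and could hold pre- or post-dose timing or extra readings. It would therefore be too strong to say that vital signs are never measured on drug.

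These points limit the claim but do not remove it. A listing is not an estimate, permission to explore is not a commitment, and the general promises of summaries are not carried into the section that should implement them.

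**Conclusion.** The point holds as a gap in the safety analysis plan. Two effects that the protocol itself raises as possible have no specified summary (blood pressure) or between-arm estimate (heart rate). For heart rate, the on-drug data needed, four Cycle 1 ECG time points per patient, are already scheduled. SAP 6.13.5 also falls short of the synopsis and SAP 6.13.

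Confidence is high for the SAP gap, which does not depend on redacted text. It is moderate for the timing of blood pressure readings, which rests on visible schedule marks and on the stated reversibility of the effect off drug. The conclusion does not extend to saying that an effect would be hidden. The primary survival analysis is not affected.

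**What to change.** - **SAP 6.13.6:** fit change in RR (or ECG heart rate) as an outcome in the mixed model already specified, with arm, timepoint, arm-by-time interaction and random patient effect, without the RR covariate. Report combination minus lomustine-plus-placebo with a 90% confidence interval at Cycle 1 Day 1 (3.5–5 h), Day 3 predose, and Day 14 predose and 3.5–5 h.
- **SAP 6.13.5:** name heart rate. Add by-arm, by-visit summaries of change from baseline in blood pressure and heart rate, with a note that readings from Cycle 2 on are nominally about 15 days after the last dose.
- **Protocol 5.6.3 and Attachment 1:** the sponsor should reconcile the statement that these effects can be monitored in the clinic with the times at which vital signs are marked. This review does not propose a monitoring schedule.

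The cost of the SAP changes is one more model and a few tables on data already collected, with no added patient burden.
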